#### .2 Methods:

- fetal heart rate tracings after the placement of CSE. Group sample sizes of 88 in each of the four groups achieves 80% power to detect a difference among the groups assuming an effect size (W) of 0.1900 using a 3 degrees of freedom Chi-Square Test with a significance level (alpha) of 0.05. The incidence of fetal heart rate changes was estimated based on data from Kinsella, et al (10). The proportion of subjects with adverse fetal heart rate changes in the low-oxytocin and fluid bolus treatment group is estimated to be 8%, and the proportion in the low-oxytocin, no-fluid bolus control group is estimated to be 23%. The proportion in the high-oxytocin groups is assumed to be 15% and 25% with and without a fluid bolus respectively. Therefore 380 patients will be enrolled to account for patient drop-out or ineligibility.
- .2.2 Subject entry, exclusion and dropout criteria: Healthy nulliparous or multiparous women with a term (>36 week gestation), singleton pregnancy in spontaneous labor or with spontaneous rupture of membranes, who request neuraxial analgesia, and will be managed by the active management of labor protocol (AMOL) and receive oxytocin, or receive oxytocin augmentation per PWH's protocols, will be eligible to participate in the study. Maternal exclusion criteria will include the presence of any systemic disease (e.g., diabetes mellitus, hypertension, preeclampsia); use of chronic analgesic medications; prior administration of systemic opioid labor analgesia; non-vertex presentation; scheduled induction of labor; or any contraindication to neuraxial analgesia.

2.3 Protocol specific methods: Eligible women will be asked to participate shortly after admission to the Labor & Delivery Unit at Prentice Women's Hospital during the routine pre-anesthetic interview. Informed, written consent will be obtained. Block randomization based on parity, via a computer generated random number table, will be performed and group assignments will be concealed in sealed, opaque envelopes. At the time of request for labor analgesia, group assignment will be determined by opening an opaque envelope. Patients will be randomized to one of four groups:

Group Assignment	Fluid Administration	Oxytocin Regimen
A	1000 mL bolus	Routine oxytocin
В	1000 mL bolus	Half-dose oxytocin
С	No bolus	Routine oxytocin
D	No bolus	Half-dose oxytocin

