The primary endpoint is the incidence of non-reassuring fetal heart rate tracings during the first 60 minutes after the placement of CSE. Cross tabulation tables will be

constructed with the presence or absence of the endpoint as rows and the groups as

06/07/07 V 1.1

10 of 11

columns. Differences in the frequency among groups will be assessed using a X statistic. Exact tests will be computed using Monte-Carlo sampling of 10,000 samples

with a confidence level of 99%.

Secondary outcomes and demographics: Age, height, weight, gestational age, fetal

station, and frequency of contractions will be compared using ANOVA or Kruskal

Wallis ANOVA with post-hoc comparisons correction for multiple comparisons.

Binominal and ordinal data will be compared between groups using the X statistic or

the Fisher's exact test. A P < 0.05 will be required to reject the null hypothesis.

5.0 Interpretation of Anticipated Results:

We anticipate that the combination of fluid administration and lower doses of oxytocin

will cause fewer adverse fetal heart rate changes in the first 60 minutes following

initiation of labor analgesia.

6.0 Budget:

.1 Materials: No additional materials will be required as all of the materials used in

the study are routinely used in the management of patients.

.2 Labor Requirements: Existing anesthesia personnel on Labor & Delivery Unit.

.3 Presentation Cost: Anticipated presentations at MARC, SOAP and ASA meetings.

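### The exact p-value for the primary 2 x 4 table is to be simulated with 10,000 draws although it can be enumerated in milliseconds, and neither the exact test nor the deciding p-value is named

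*Combined protocol and SAP*

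**What the plan says.** In section 4.0, .2 Data evaluation, the primary endpoint is cross-tabulated by group, giving a 2 x 4 table, and the groups are compared with a chi-square statistic. The next sentence reads "Exact tests will be computed using Monte-Carlo sampling of 10,000 samples" and goes on to specify a 99% confidence level, most naturally the interval around the simulated p-value.

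The threshold appears in two places. The sample-size paragraph in section 3.0, .2 Methods, plans the trial "using a 3 degrees of freedom Chi-Square Test with a significance level (alpha) of 0.05". The paragraph on secondary outcomes and demographics in section 4.0 closes with "A P < 0.05 will be required to reject the null hypothesis".

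The plan does not give a random seed, the name of the exact test, a rule for a 99% interval that contains 0.05, or a statement of which p-value decides if the asymptotic and exact values fall on opposite sides of 0.05.

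**The concern.** Monte-Carlo sampling is a way to approximate an exact p-value when the full set of tables is too large to list. Here the set is small, so the sampling adds noise to the primary p-value and brings nothing in return. If the simulated value decides, two analysts with the same four event counts and different seeds could report opposite verdicts for a result near 0.05.

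A related gap is larger in size. An exact test on a 2 x 4 table can order the tables by the Pearson statistic or by their probability (Fisher-Freeman-Halton). These are different tests with different p-values, and more draws do not bring them together. The plan's wording allows either, and allows either to stand beside the asymptotic chi-square value. At stake is whether the verdict on the single primary comparison can be reproduced from the table alone, without a choice made after the data are seen.

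**Working it through.** **Inputs.** From section 3.0, .2 Methods: 88 per group in four groups (352 women); event rates of 8% (low oxytocin, bolus), 23% (low oxytocin, no bolus), 15% (high oxytocin, bolus) and 25% (high oxytocin, no bolus); 3 degrees of freedom; alpha 0.05. From section 4.0: 10,000 draws, 99% level.

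**1. The plan's own figure.** The plan states "Group sample sizes of 88 in each of the four groups achieves 80% power".
- Mean rate: (8 + 23 + 15 + 25)/4 = 17.75%.
- Squared deviations: 0.00951 + 0.00276 + 0.00076 + 0.00526 = 0.01828.
- W² = (0.01828/4)/(0.1775 x 0.8225) = 0.0313, so W = 0.1769.
- Noncentrality: 352 x 0.0313 = 11.0. Power on 3 degrees of freedom is 80.4%, and 88 is the smallest group size that reaches 80%.

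The stated size therefore follows from the four rates. The printed effect size of 0.1900 would give 86.2% power at 88 per group. That is a separate matter and does not bear on this point.

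**2. Simulation error at 0.05.**
- Standard error: sqrt(0.05 x 0.95/10,000) = 0.00218.
- 99% half-width: 2.576 x 0.00218 = 0.0056, a band of about 0.0444 to 0.0556.

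The chance that a simulated p-value from 10,000 draws is below 0.05 follows from the binomial distribution:

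| True exact p | Chance simulated p < 0.05 |
|---|---|
| 0.045 | 99% |
| 0.048 | 82% |
| 0.049 | 67% |
| 0.051 | 32% |
| 0.052 | 18% |
| 0.055 | 1% |

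**3. Tables near the threshold (88 per group).** For 7, 14, 19 and 19 events the total is 59 and the sum of squares is 967.
- Chi-square = (967 - 59²/4)/(88 x 0.1676 x 0.8324) = 96.75/12.28 = 7.88.

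| Events | Asymptotic p | Exact Pearson p | Fisher-Freeman-Halton p |
|---|---|---|---|
| 7/14/19/19 | 0.0486 | 0.0502 | 0.0373 |
| 8/16/17/22 | 0.0505 | 0.0499 | 0.0408 |
| 10/14/15/24 | 0.0440 | 0.0452 | 0.0516 |

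For the first table, a 10,000-draw exact Pearson p-value is below 0.05 with probability 0.46. For the second, 200 seeds gave values from 0.0449 to 0.0558, and 55.5% of them were below 0.05. In the first table the two exact tests differ by 0.0502 - 0.0373 = 0.0129, more than twice the simulation half-width.

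**4. Cost of enumeration.** The first table has 37,820 tables with the same margins and the second 45,760. Each was listed in full in under 0.01 seconds.

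**5. How often it matters.** 200,000 simulated trials at the planned rates, and 200,000 at a common rate of 17.75%:

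| | Planned rates | No difference |
|---|---|---|
| Exact Pearson p within 0.0444 to 0.0556 | 2.6% | 1.0% |
| Simulated verdict differs from exact | 0.40% | 0.16% |
| Two seeds disagree | 0.56% | 0.23% |
| Asymptotic and exact verdicts differ | 0.51% | 0.20% |
| Rejects, asymptotic | 83.4% | 5.00% |
| Rejects, exact by enumeration | 83.0% | 4.81% |
| Rejects, simulated exact | 83.0% | 4.81% |

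The 83.4% is simulated power. The 80.4% in step 1 is the noncentral chi-square approximation for the same rates.

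**The case against.** The case on the other side has four parts.

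- **The plan does not say that the simulated p-value decides.** A reader might infer from the sentence on Monte-Carlo sampling that the primary verdict rests on it. The text does not support that: the chi-square statistic is the named assessment and the trial is sized on it. The passage can be read as one test whose p-value is found by simulation, or as a chi-square test with a supporting exact value. The seed matters only on the first reading, and a choice between two p-values arises only on the second. This stands, which is why the point is conditional.
- **The plan does address simulation error.** It sets a 99% confidence level, so it would be wrong to say that the error is ignored. This stands too. What is missing is a rule for an interval that contains 0.05.
- **The effect is very small.** This stands. The tables in step 3 were chosen at the boundary. Counts close to the planned rates (7, 13, 20 and 22 events) give an exact p-value of 0.0115, well outside the band, and a result of 0.049 should hardly be interpreted differently from one of 0.051.
- **Monte-Carlo exact testing is valid, so a preference for enumeration is a matter of taste.** The first half is right. The second half is not, because for a table of this size enumeration costs nothing and removes the noise entirely.

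**Conclusion.** The point holds as a minor, free improvement. If the simulated value decides, 10,000 draws leave avoidable noise in the primary p-value, enough to change the verdict in about 0.4% of trials at the planned rates. The unnamed exact test and the unnamed deciding p-value matter more in a borderline table, since no number of draws settles them.

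A reader might infer that the trial's error rates are at risk. They are not. Rejection under no difference is 4.81% and power 83.0% whether the exact p-value is simulated or enumerated, and even taking the smaller of the asymptotic and exact Pearson values gives a type I error of about 4.97%.

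These figures assume 88 women analysed per group, an exact test conditional on both margins, the exact Pearson test as the reference, and a simulated p-value equal to the count divided by 10,000. The documents name no analysis software, so the assumption that enumeration is available should be checked. Any general-purpose programming language can do it.

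**What to change.** Replace the Monte-Carlo sentence in section 4.0, .2 Data evaluation, with text such as:

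*The primary p-value is the exact p-value of the Pearson chi-square statistic for the 2 x 4 table, conditional on both margins and computed by complete enumeration. It alone decides the primary hypothesis at 0.05. The asymptotic p-value is descriptive.*

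If the software offers only simulation, use at least 1,000,000 draws with a seed stated in advance. The 99% half-width at 0.05 then falls to 2.576 x sqrt(0.05 x 0.95/1,000,000) = 0.00056. The seed is still needed: the 7/14/19/19 table lies only 0.0002 from the threshold.

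The change is one sentence and seconds of computing, with no effect on sample size, data collection or care. Letting the exact value decide over the asymptotic chi-square costs 0.4 to 0.5 points of power (83.4% to 83.0% above; 83.5% to 83.0% in a separate run of 4,000 trials). If the sponsor prefers the asymptotic test, which is the one used for the sample size, the sentence should say that it decides and that the enumerated exact value is supportive. Either choice is sound once it is fixed before the data are seen.

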One of the proposed mechanisms for non-reassuring fetal heart tracings after initiation of analgesia is that the pain relief from neuraxial analgesia causes a decrease in catecholamine release by the sympathetic nervous system (4). The subsequent decrease in the circulating epinephrine concentration contributes to an increase in uterine tone, as epinephrine is a potent tocolytic agent. The increased tone, in turn, leads to a decrease in placental blood flow, and eventually fetal bradycardia. Prior to initiation of neuraxial analgesia, an intravenous fluid bolus is usually given in order to prevent hypotension due to the sympathectomy associated with the neuraxial administration of local anesthetic. The fluid bolus mitigates hypotension due to relative hypovolemia. However, it may also dilute oxytocin (both from endogenous and exogenous sources), or decrease endogenous release of oxytocin, thus decreasing the risk of uterine hyperstimulation. Preliminary evidence suggests that peri-analgesia fluid management influences uterine activity and fetal heart rate patterns (10,11) In an underpowered study, Kinsella suggested that a fluid bolus may be associated with a decreased incidence of non-reassuring fetal heart rate patterns (10). Cheek and colleagues demonstrated a decrease in uterine activity associated with a 1 L, compared to 0.5 L or no fluid bolus before initiation of epidural analgesia (11). A Cochrane database review of the literature found that intravenous preloading may help to reduce maternal hypotension, but using lower doses of local anesthetic and opioid-only blockade also reduces the incidence of hypotension and may reduce or

06/07/07 V 1.1 eliminate the need for preloading to prevent maternal hypotension (1). There were no differences between preloading and no-preloading with regards to fetal heart rate abnormalities, however, the wide confidence intervals could not refute or confirm a difference (1). Therefore, the administration of a fluid bolus prior to the initiation of neuraxial analgesia remains controversial and many institutions do not routinely administer a bolus.

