### Fetal heart rate monitoring:

Fetal heart rate monitoring and frequency of uterine contractions will be recorded by external tocodynamometry.

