# Fetal heart rate tracing assessment:

Fetal heart rate tracings will be examined for 30 minutes before and 60 minutes after the initiation of analgesia by a perinatologist blinded to study group off-line after delivery. NICHD guidelines (12) will be used to assess FHR patterns. Non-reassuring FHR patterns will be defined as any one or more of the following: minimal or absent variability, late decelerations, and persistent deceleration (see Appendix).

.2.4 Risks/Benefits: All of the techniques and medications used in this study are routinely used for CSE analgesia during labor and for management of labor. The risks of the CSE procedure itself are unchanged by participating in this study. These risks include: epidural analgesia may not be effective, the epidural procedure may need to be repeated, pruritus, nausea, vomiting, or hypotension. Less common risks include maternal postdural puncture headache. Rare complications include maternal or fetal respiratory depression, total spinal anesthesia, a toxic reaction to the anesthetic agents, and bleeding or infection in

the epidural or spinal space that may lead to nerve damage. The risk of oxytocin administration includes nausea, vomiting, confusion, allergic reaction, uterine hyperstimulation, fetal bradycardia, or maternal cardiac arrhythmias. There are

no direct benefits to the patient for participating in the study.

4.0 Data Analysis:

.1 Data collection form: The following data will be collected:

Demographic data: age, race, height, weight, gravidity, parity, and gestational age.

history of prior inductions.

Labor data: time of rupture of membranes, cervical examination prior to placement of CSE (dilation, effacement, and station); start and stop time of fluid bolus, time of intrathecal injection, oxytocin dose at time of placement of CSE, vasopressor use and dose, maximum oxytocin dose in 60 minutes following placement of CSE, number of times oxytocin infusion is stopped or decreased for hyperstimulation or nonreassuring fetal status, time to complete cervical dilation, time of delivery, maximal

maternal body temperature in study period.

Mode of delivery: normal spontaneous vaginal, instrumental vaginal, Cesarean.

Neonatal data: 1- and 5-minute Appar scores; fetal umbilical cord gases (if taken);

birth weight; neonatal sepsis workup or ICU admission.

Fetal heart rate tracing data: see appendix

.2 Data evaluation:

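### Contraction frequency, if meant as a post-CSE secondary outcome, has no stated time window and no baseline adjustment, so its planned comparison is valid but gives up precision

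*Combined protocol and SAP*

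**What the plan says.** Section 4.0, Data evaluation, has one list for secondary outcomes and demographics. It contains age, height, weight, gestational age, fetal station and contraction frequency. All six are compared across the four groups by ANOVA or Kruskal "Wallis ANOVA with post-hoc comparisons correction for multiple comparisons". No covariate is named, and no time window is given for contractions.

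Two other places bear on what data exist. Under Fetal heart rate monitoring: "Fetal heart rate monitoring and frequency of uterine contractions will be recorded by external tocodynamometry". Under Fetal heart rate tracing assessment: "Fetal heart rate tracings will be examined for 30 minutes before and 60 minutes after the initiation of analgesia".

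The Background ties both interventions to uterine activity. Oxytocin is given to raise contraction frequency and strength. Fluid may dilute oxytocin or reduce its release, "thus decreasing the risk of uterine hyperstimulation". The Background also has fluid acting by limiting maternal hypotension.

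On timing, the envelope is opened when the woman requests analgesia (Protocol specific methods). Oxytocin in groups B and D is halved at that same point (Oxytocin Management). The bolus in groups A and B starts at positioning for CSE (Fluid Management). Both interventions therefore begin before the intrathecal injection. The data form in section 4.0 records the bolus times and the injection time, but no request or envelope-opening time.

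**The concern.** Women join the trial in different labour patterns and on different oxytocin rates, and the half-dose arms halve whatever rate is running. Contraction frequency before treatment will plausibly differ between women and carry over into the following hour. An unadjusted four-group comparison leaves all of that variation in the error term. Part of it could be removed with the woman's own earlier value, if a usable stretch of tracing precedes treatment.

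At stake is the precision of a secondary comparison. If the primary result is null or unclear, contraction frequency is one of the few planned measures that could show whether either intervention altered uterine activity. An interval wider than necessary makes that harder to judge.

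**Working it through.** **Inputs from the plan.** The only power statement concerns the binary primary endpoint: "Group sample sizes of 88 in each of the four groups achieves 80% power to detect a difference among the groups". The printed W is 0.19, the test is a chi-square on 3 df, and α is 0.05. The assumed rates are 8%, 23%, 15% and 25%. Enrolment is 380, which allows for 1 − 352/380 = 7.4% loss. No SD, target difference or pre/post correlation is given for contraction frequency.

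**Reproducing the plan's figure.** The mean rate is 0.1775. W² = mean squared deviation / [0.1775 × 0.8225] = 0.004569 / 0.145994 = 0.0313, so W = 0.177. With N = 4 × 88 = 352, a noncentral chi-square on 3 df gives 80.4% power, and 88 per group is the smallest size that reaches 80%. The sample size and power therefore reproduce from the rates. The printed W of 0.19 would give 86.2% power and need only 76 per group; that is a separate matter and plays no part below. N = 352 is carried forward.

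**Gain from a clean baseline.** Take the effect that the unadjusted four-group ANOVA detects with 80% power at N = 352, α = 0.05. Solving the noncentral F gives Cohen f = 0.177, so the noncentrality is 352 × f² = 11.03. This f is a reference point chosen for the comparison and is not a plan figure; its closeness to W above is expected, since both describe about 80% power on 3 df at the same N. ANCOVA on a pre-treatment value with correlation ρ multiplies the residual variance by 1 − ρ². The noncentrality becomes 11.03/(1 − ρ²), with 3 and 347 df.

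| ρ (assumed) | Variance factor | SE factor | Equivalent N = 352/(1 − ρ²) | Noncentrality | Power |
|---|---|---|---|---|---|
| 0 (unadjusted) | 1.00 | 1.000 | 352 | 11.03 | 80.0% |
| 0.2 | 0.96 | 0.980 | 367 | 11.49 | 81.8% |
| 0.3 | 0.91 | 0.954 | 387 | 12.12 | 84.0% |
| 0.5 | 0.75 | 0.866 | 469 | 14.70 | 90.8% |
| 0.7 | 0.51 | 0.714 | 690 | 21.62 | 98.2% |

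A single 1-df contrast (half-dose against routine oxytocin, 176 v 176, difference 0.30 SD) behaves the same way: 80.4% unadjusted, then 83.9%, 90.1% and 97.6% at ρ = 0.3, 0.5 and 0.7.

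**Loss from a contaminated baseline.** Suppose a share s of the 30-minute pre-CSE window falls after the oxytocin change and already shows the full effect (both are assumptions). The baseline then differs between arms by s times the effect, and with equal variances the adjusted effect shrinks by the factor 1 − ρs. At ρ = 0.5 and s = 0.5:

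- effect factor = 1 − 0.25 = 0.75
- standardised difference = 0.30 × 0.75 / 0.866 = 0.260
- 0.260 × √(176/2) = 2.44, and Φ(2.44 − 1.96) = about 68%

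That is below the unadjusted 80.4%. At ρ = 0.5 adjustment breaks even when 1 − 0.5s = 0.866, that is s = 0.27, or about 8 of the 30 minutes.

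**The case against.** The strongest objection is that the plan never calls contraction frequency a post-CSE outcome. The other five variables in the list are baseline characteristics, and station is recorded before CSE. If contraction frequency is there only to check comparability of the groups, adjusting it for baseline has no meaning. This stands as a real ambiguity and is why the point is conditional. It does not remove the point: the list is headed as covering secondary outcomes, and contraction frequency is the only item in it that could plausibly be one. If only a baseline check was intended, the plan states no analysis of contraction frequency after CSE, and the change below would supply one.

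A reader might infer that the 30 minutes before analgesia give a ready-made pre-treatment value. The documents do not support that. The interval from request to CSE is not stated, and if it reached 30 minutes the window would contain no untreated tracing. The window is also described for fetal heart rate, and the appendix listing the tracing data is not in the available text. Nothing here claims that earlier contractions go unrecorded.

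A reader might also take contraction frequency as the route by which both treatments work. That is too strong: fluid is also meant to act through hypotension, and oxytocin through contraction strength and tone.

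Finally, the size is wholly assumed, and a short pre-request segment is a noisy baseline that pulls ρ down. That is correct, and the lower rows of the range should be taken seriously.

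**Conclusion.** The point holds as an efficiency improvement to a secondary analysis, on the reading that contraction frequency is a post-CSE outcome. No baseline adjustment is planned, and adjusting for a value that truly precedes treatment would raise power from 80% to somewhere between about 82% (ρ = 0.2) and 98% (ρ = 0.7). At ρ of 0.3 or less the gain is at most about 4 percentage points. These figures assume 352 analysed women, the ANOVA form of the test and an effect set to give 80% unadjusted power.

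It would be wrong to conclude that the planned comparison is biased or invalid. Under randomisation the unadjusted test is sound, and the primary chi-square analysis is untouched. Adjustment helps only if the baseline precedes the opening of the envelope; using the full pre-CSE window could leave the trial worse off than no adjustment.

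**What to change.** In section 4.0, Data evaluation:

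- Separate contraction frequency from the demographics and define the outcome as contractions per 10 minutes over the 60 minutes after CSE.
- Analyse it by ANCOVA with group and the woman's own contraction frequency from tracing before the envelope is opened. Keep the existing multiple-comparison correction, applied to the adjusted means.
- If residuals are clearly non-normal, use a rank-based ANCOVA in place of Kruskal-Wallis.
- State that the whole 30-minute pre-CSE window is not the baseline.
- Keep women without usable pre-request tracing in the analysis, using mean imputation of the baseline with a missing-value indicator.

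On the data form, add the time at which the envelope is opened.

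The cost is a few sentences of analysis text, one time field, and the counting of contractions in one earlier segment of a tracing that is already recorded. No extra women or procedures are needed. The downside is that a short pre-request segment may be noisy, so the gain may be small.
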